15.3.5 Definition of a suspected unexpected serious adverse reaction

A suspected unexpected serious adverse reaction (SUSAR) is any SADR whose nature or intensity is not consistent with the current version of the IB or the respective SmPC for comparators.

15.3.6 Definition of adverse events of special interest

Adverse events of special interest include pIMDs occurring during the 6 months safety follow-up period (Section 14.1.5 and 15.3.11).

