10.1.1 Primary endpoints

- Type and incidence of AEs and SAEs from the time of first study drug administration (Visit 2) until the last visit to the clinic (Visit 4 for group 1 to 4 and Visit 3 for group 5 to 6).
- Type and incidence of SAEs and AEs of special interest during the 6 months safety follow-up.
- Frequency and severity of administration-site reactions as assessed by an independent evaluator with help from study subject before study drug administration and 15 minutes and 120 minutes after study drug administration. Administration-site reactions to be recorded are swelling, redness, pain and pruritus in the administration area (nose or arm). Reactions are classified as none, mild, moderate or severe. The administration-site reactions pain and pruritus will also be recorded by the subject in an electronic diary for 10 days starting in the evening the day after each treatment and classified as none, mild, moderate or severe.
- Frequency of solicited AEs. The subjects will record the occurrence of solicited AEs in an electronic diary for 10 days after study drug administration. Solicited AE include runny nose, nasal congestion, sneezing, fever (i.e., temperature >38°C), chills, sweating, headache, tiredness, muscle aches, joint pain, cough, sore throat, nausea.
- Frequency of clinically significant changes in ECG, vital signs, physical examination findings and laboratory variables from baseline to the last visit to the clinic.

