11. STUDY DESIGN

This is a Phase I/II, randomised, partially double-blind (group 1 to 4), parallel-group study designed to evaluate the safety, tolerability and immune response following Immunose FLU vaccination at 2 sites in Sweden.

Consenting subjects will be assessed for eligibility at the screening visit (Visit 1) within 6 weeks prior to randomisation. Eligibility will be re-confirmed prior to each dose.

A total of 162 subjects will be randomised to one of 6 treatment groups in a 2:2:2:1:1:1 ratio on Day 0 (Visit 2) as follows:

- **Group 1:** Immunose FLU 1%, containing 15 µg HA/strain and 1% Endocine for intranasal administration (n=36)
- **Group 2:** Immunose FLU 2%, containing 15 µg HA/strain and 2% Endocine for intranasal administration (n=36)
- **Group 3:** Influenza antigen, containing 15 µg HA/strain for intranasal administration (n=36)
- **Group 4:** Saline (NaCl) for intranasal administration (n=18)
- **Group 5:** ██████████, containing 15 µg HA/strain for intramuscular administration (n=18)
- **Group 6:** ██████████, containing $10^{7.0\pm 0.5}$ FFUs for intranasal administration (n=18)

Subjects in group 1 to 4 will receive treatment in a partially double-blinded fashion via intranasal administration on Day 0 (Visit 2) and on Day 21+7 (Visit 3), see Table 1. Since the visual appearance of the study drugs may differ, there is a risk that the administering nurse will be unblinded. Therefore the pre- and post-treatment inspection of the administration site will be performed by an independent evaluator. The same independent evaluator will perform both pre- and post-dose assessments. For further details on blinding, refer to Section 13.10.

For subjects in group 1 to 4 there will be a total of 4 visits to the clinic; Visit 1 (screening), Visit 2 (Day 0), Visit 3 (Day 21+7) and Visit 4 (Day 42+7). Telephone contacts will be taken approximately every 8th week after the last visit to the clinic (Visit 4) for collection of any AEs of special interest or SAEs that may have occurred after Visit 4 during a 6 months safety follow-up period starting from the day of the last vaccination. For details on the follow-up phase, refer to Section 15.3.11.

Subjects in group 5 and 6 will receive treatment in an unblinded fashion via a single intramuscular (group 5) or single intranasal (group 6) administration on Day 0 (Visit 2), see Table 3. No treatment will be given on Day 21+7 (Visit 3).

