For subjects in group 5 and 6 there will be a total of 3 visits to the clinic; Visit 1 (screening), Visit 2 (Day 0), and Visit 3 (Day 21+7). Telephone contacts will be taken approximately every 8th week after the last visit to the clinic (Visit 3) for collection of any AEs of special interest or SAEs that may have

occurred after Visit 3 during a 6 months safety follow-up period starting from the day of the last vaccination.

In all groups, safety and tolerability, including local tolerability, will be assessed. Local tolerability (swelling and redness [assessed by the independent evaluator] and pain and pruritus [assessed by the subject]) will be assessed before and after each treatment with study drug (Visit 2 and 3 for group 1 to 4 and Visit 2 for group 5 to 6). Safety and tolerability will be assessed by vital signs (blood pressure and heart rate), physical examination, 12-lead electrocardiogram (ECG), collection of AEs and laboratory tests (haematology, clinical chemistry and urinalysis) at time points specified in Table 1 to Table 4. Subjects with suspected influenza will be tested to confirm presence and strain of the influenza virus.

Local tolerability will also be assessed by the subjects' recording of the presence or absence of local administration site reactions (pain and pruritus) and solicited AEs (runny nose, nasal congestion, sneezing, fever [temperature >38°C], chills, sweating, headache, tiredness, muscle aches, joint pain, cough, sore throat, nausea) in an electronic diary for 10 days after each dosing occasion, starting in the evening the day after treatment.

[figure not shown]
Immune responses against the vaccine antigens will be evaluated in both nasal and blood samples. Influenza-specific immune responses will be evaluated in nasal samples (IgA) and in serum (HI and VN) and PBMC (T-cells) from blood samples. Blood samples for peripheral blood mononuclear cell (PBMC) preparation and subsequent T-cell analysis will be taken from 10 subjects per treatment group at the same time points as the other immunology blood samples. Sampling for immunology analyses at visits and time points specified in Table 1 to Table 4.

The total study duration for the subjects in the study will be up to 36 weeks (group 1 to 4) and 33 weeks (group 5 and 6) including a 6 week screening period and a 180 days follow-up period after the last vaccination.

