Further details on the investigational medicinal products are provided in Section 13.1. Procedures for maintaining the blind is described in Section 13.10. Randomisation procedures are outlined in Section 13.7.

Safety assessments are described in detail in Section 15 and efficacy assessments are described in Section 16.

Figure 1 Study flowchart and blood sampling schedule

¹ Telephone follow-up approximately every 8th week ±7 days following the last visit to the clinic for a total of 3 occasions during 180 days starting after the last vaccination.

² Nasal swab for group 1 to 4 at Visit 3 will be performed at least 60 minutes prior to the pre-dose administration site inspection for local tolerability assessments.

Table 1 Schedule of events group 1 to 4

Day (+/- visit window) Week (+/- visit window)	Visit 1 Screening	Visit 2	Visit 3 ¹	Visit 4 ¹	Safety follow-up (telephone calls)		
	Day -42 to Day -1 Week-6 to week-1	Day 0 Week 0	Day 21 (+7) Week 3 (+1 week)	Day 42 (+7) Week 6 (+ 1 week)	Day 81±7 Week 11 (±1 week)	Day 141±7 Week 20 (±1 week)	Day 201 ±7 Week 28 (±1 week)
Informed consent	X						
Eligibility criteria ²	X	X ²	X ²				
Demographics	X						
Medical history	X						
Physical examination	X			X			
Weight and height	X						
Electrocardiogram (ECG)	X			X			
Pregnancy test (urine dipstick) ³	X ³	X ³	X ³				
HIV, Hepatitis B and C blood sampling	X						
Urine drug screen	X						
Haematology and clinical chemistry blood sampling	X			X			
Urinalysis sampling	X			X			
Prior and concomitant medications	X	X	X	X			
Randomisation		X					
Diary instructions		X					
Diary check-up							
AEs ^{4,5}		X ⁴	X	X	X ⁵	X ⁵	X ⁵
Vital signs ⁶	X	X ⁶	X ⁶	X			
Nasal swab ⁷	X		X ⁷	X			
Immunology blood sampling ⁸		X ⁸	X ⁸	X ⁸			
Administration site inspection for local tolerability ⁹		X ⁹	X ⁹				
Dose administration ¹⁰		X ¹⁰	X ¹⁰				

¹ At least 3 weeks between Visit 2 and Visit 3 and between Visit 3 and Visit 4.

² Continued eligibility criteria are defined in Section 12.6.

³ Pregnancy test should be performed in females at screening and pre-dose at Visit 2 and Visit 3.

⁴ Pre-treatment events will be collected from signing of the ICF until first dose and AEs will be collected post study drug administration.

⁵ SAEs and AEs of special interest (Section 14.1.5).

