15.3.11 Safety follow-up

SAEs and AEs of special interest will be collected during 6 months after the last vaccination through telephone calls approximately every 8th week ± 7 days following the last visit to the clinic for a total of 3 occasions (see Section 14.1.5).

The following will be collected:

- pIMDs, i.e. a subset of AEs that include both clearly autoimmune diseases and also other inflammatory and/or neurologic disorders which may or may not have an autoimmune aetiology.
- SAEs

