15.3.12 Reporting period for adverse events

Collection of pre-dose events starts after the subject has signed the ICF and continues until the first administration of IMP.

Collection of AEs starts upon administration of the first dose of IMP and continues until the subject's last visit to the clinic (Visit 4 for group 1 to 4 and Visit 3 for group 5 and 6).

Any apparent side effects experienced by the subject will be assessed from the time the subject signs the informed consent and throughout the last visit to the clinic.

In addition, SAEs and AEs of special interest will be documented during the 6 months follow-up period (Section 15.3.11).

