18.5.2.1 Adverse Events

All AEs will be coded using the medical dictionary for regulatory activities (MedDRA). Data will be summarised using preferred term (PT) and primary system organ class (SOC) and presented by treatment group and in total.

Nature, incidence, severity and the Investigator's causality assessments will be reported for each AE. AEs, SAEs, drug-related AEs, AEs leading to withdrawal and AEs of special interest will be listed and summarised by incidence and treatment group.

Pre-treatment events, collected from the signing of the ICF until the first dose, will be listed and summarised by incidence and treatment group.

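### In Groups 1 to 4, a potential immune-mediated disease that begins between the two doses is left out of the count of AEs of special interest, because that count starts at the last vaccination

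*Combined protocol and SAP*

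**What the plan says.** Section 15.3.6 defines the class: "Adverse events of special interest include pIMDs occurring during the 6 months safety follow-up period". The second primary endpoint in Section 10.1.1, repeated in the synopsis, is "Type and incidence of SAEs and AEs of special interest during the 6 months safety follow-up".

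The start of that period is given in several places. Section 15.3.11, to which the definition refers, says that "SAEs and AEs of special interest will be collected during 6 months after the last vaccination". Section 11 describes the calls in Groups 1 to 4 as collecting events "that may have occurred after Visit 4 during a 6 months safety follow-up period starting from the day of the last vaccination", and uses the parallel wording "occurred after Visit 3 during a 6 months safety follow-up period starting from the day of the last vaccination" for Groups 5 and 6. The first footnote to Figure 1 puts the length at 180 days, counted from the last vaccination.

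Groups 1 to 4 receive two doses 3 to 4 weeks apart (Section 13.5.1). Groups 5 and 6 receive one dose on Day 0.

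Ordinary AEs are covered earlier. Under Section 15.3.12, "Collection of AEs starts upon administration of the first dose of IMP", and it runs to the last clinic visit. These events form the first primary endpoint. Section 18.5.2.1 then provides that "AEs, SAEs, drug-related AEs, AEs leading to withdrawal and AEs of special interest will be listed and summarised by incidence and treatment group". It gives no AESI definition or window of its own.

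**The concern.** The AESI class singles out pIMDs in the first clinical use of this antigen and adjuvant combination (Section 9.4), and AESI incidence is part of a primary safety endpoint. A reader of the AESI table would expect it to hold every pIMD after first exposure. As worded, in a subject who receives both doses it begins at dose 2, and onset in the weeks after dose 1 is outside it.

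Nothing in the text provided repairs this later. No section names a second AESI window or asks for pIMDs to be marked among the clinic-phase AEs, and pIMDs are described only in general terms (Sections 14.1.5 and 15.3.11), without a list of terms. Clinic-phase data are analysed unblinded before the follow-up ends (Section 18.3). Unless a rule is set first, picking out early pIMDs afterwards would be a judgement made with treatment known.

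**Working it through.** No power calculation is involved (Section 18.2 says there was none), so the check is date arithmetic.

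**Inputs**
- Dose 2 in Groups 1 to 4: Day 21 to Day 28 (Table 1, Section 13.5.1).
- Follow-up: 180 days from the last vaccination (Section 11, footnote to Figure 1).
- Calls: Days 81, 141 and 201 in Table 1; Days 60, 120 and 180 in Table 3.
- Group sizes: 36 in each of Groups 1 to 3 and 18 in Group 4, so 3 × 36 + 18 = 126 (Section 13.7.1).

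**Reproducing the plan's own figure**
- Dose 2 on Day 21 plus 180 days is Day 201, the last call in Table 1.
- All three calls fit: 21 + 60 = 81, 21 + 120 = 141, 21 + 180 = 201.
- The alternative anchor, every 8 weeks (56 days) from Visit 4 on Day 42, gives Days 98, 154 and 210, which does not match.

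The schedule is therefore anchored at the last vaccination.

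**Time after dose 1 outside the AESI window, Groups 1 to 4, both doses given**
- Dose 2 on Day 21: 21 / (21 + 180) = 21/201 = 10.4%.
- Dose 2 on Day 28: 28 / (28 + 180) = 28/208 = 13.5%.
- Per group of 36: 36 × 21 = 756 to 36 × 28 = 1,008 person-days.
- Over 126 subjects: 126 × 21 = 2,646 to 126 × 28 = 3,528 person-days, about 7.2 to 9.7 person-years.

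In Groups 5 and 6 the first dose is the last, so the uncovered time is 0 days.

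**Window if AESIs were counted from the first dose**
- Groups 1 to 4: 201 to 208 days.
- Groups 5 and 6: 180 days.

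**Call timing (editorial)**
- Every 8 weeks from the last clinic visit gives Days 98, 154 and 210 against 81, 141 and 201 in Table 1.
- The same rule from Visit 3 on Day 21 gives Days 77, 133 and 189 against 60, 120 and 180 in Table 3.
- The differences are 17, 13 and 9 days in both tables.

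**The case against.** The strongest reply is that the two primary endpoints are complementary. All AEs and SAEs are collected from first dose to last clinic visit; after that only SAEs and AESIs are. On this view the AESI label is a filter for what is still collected once general collection stops, and Section 9.5 says the long follow-up is there for late-occurring immune-mediated disease. This stands in part. An inter-dose pIMD is in the first primary endpoint and is tabulated by preferred term and system organ class. But Section 18.5.2.1 promises an AESI summary as well, and that summary omits the event.

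A second reply is that Section 15.3.6 says include, which is not exhaustive, and that Section 18.1 leaves variable definitions to a separate SAP. That SAP could close the gap, but it is not in the text provided. The protocol endpoint is itself restricted to the follow-up, and no other AESI window is named.

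Three stronger readings are tempting and are not supported:
- *Comparison with Groups 5 and 6 is distorted.* All groups share the same 180 days after the last vaccination, and safety comparisons are descriptive (Section 18.5.2). Counting from first dose is what would make the windows unequal.
- *The same event changes class if dose 2 is withheld.* This follows only if dose 1 then becomes the last vaccination. No section says so: Section 12.4 equates the last vaccination with Visit 3 in Groups 1 to 4, and Table 1 fixes the call days.
- *Everything up to the last clinic visit is excluded, 42 to 49 days in Groups 1 to 4.* The Section 11 wording about events after Visit 4 or Visit 3 describes what the calls collect. The Table 1 footnote, "SAEs and AEs of special interest (Section 14.1.5", marks the call cells but is also on the row label, and its absence from the Visit 2 to 4 cells most naturally means that all AEs are collected there.

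**Conclusion.** The point holds as a minor one. For a Group 1 to 4 subject who receives both doses, a pIMD with onset in the 21 to 28 days between them (10.4% to 13.5% of the time from dose 1 to 180 days after dose 2) is outside the AESI endpoint and summary. The defect is the completeness of the AESI count after first exposure.

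A reader might infer that safety events go unrecorded or that the adjuvant comparison is compromised. Neither follows: the event is captured as an AE or SAE, and the Endocine contrast within Groups 1 to 4 uses the same window in every arm.

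The person-time figures assume that all 126 subjects receive dose 2. The documents give no pIMD rate, so no expected number of omitted events can be stated. The case also requires dose 2 to be given after such an onset. The documents leave that open: the continued eligibility criteria in Section 12.6 do not name pIMDs, and Section 12.8.1 leaves discontinuation for an AE to the Investigator's opinion.

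**What to change.** - In Sections 15.3.6 and 10.1.1 and in the synopsis, define an AESI as any pIMD with onset from first study drug administration to 180 days after the last vaccination, in all groups.
- Add a pIMD flag to the AE form, and settle it for clinic-phase AEs before the code is broken.
- Tabulate clinic-phase and follow-up pIMDs together across the CSR and its addendum.
- Keep the count for the 180 days after the last vaccination beside the full count, because the full windows differ between Groups 1 to 4 and Groups 5 and 6.
- Editorial: reconcile with the start at last vaccination (a) Section 15.3, which labels it as Visit 3 or Visit 4 where Section 12.4 has Visit 3 for Groups 1 to 4 and Visit 2 for Groups 5 and 6; (b) the after-Visit-4 and after-Visit-3 wording in Section 11; and (c) the 8-weekly wording in Sections 11, 14.1.5 and 15.3.11, which must also agree with the call days in Tables 1 and 3.

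The cost is wording, one form field and one combined table with a second count. No new visits or data collection are needed, since clinic-phase AEs are already recorded.

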15.3.7 Rating scales

15.3.7.1 Intensity

The expression intensity of adverse events means the intensity of the event in the opinion of the subject. The grades of intensity are defined as follows:

Mild: Does not interfere with the subject's daily activities and requires no or minimal medication.

Moderate: Interferes with the subject's daily activities and may require medication.

Severe: Interrupts the subject's daily activities markedly and requires medical consultation.

The intensity of each AE is to be graded as above by the Investigator.

15.3.7.2 Causality

The relationship between the IMP and each AE has to be classified by the Investigator using one of the following terms:

Unlikely: The onset of the AE and administration of IMP are such that the medication is not likely to have any reasonable association with the AE.

Possible: It might be possible that the AE could have been caused by the IMP.

Probable: It is probable that the AE is caused by the IMP.

15.3.8 Assessment of outcome

The Investigator must assess the outcome of an AE using the definitions below:

Recovered: the subject has recovered completely, and no symptoms remain.

Recovering: the subject's condition is improving, but symptoms still remain.

Recovered with sequelae: the subject has recovered, but some symptoms remain (for example, the subject had a stroke and is functioning normally, but has some motor impairment).

Not recovered: the subject's condition has not improved and the symptoms are unchanged (for example, an atrial fibrillation has become chronic).

Death

15.3.9 Reporting procedures for serious adverse events

Starting from administration of the first dose of IMP, all SAEs must be reported by the Investigator to the Sponsor and to PCG within 24 hours after awareness of the SAE.

The SAE reporting will be performed electronically via the eCRF. The site staff will enter all available information regarding the SAE in the AE log for the specific subject. As soon as the event is saved as serious in Viedoc™, an e-mail alert will be sent to predefined recipients to highlight that an SAE has occurred.

A designated person at PCG will review the SAE report to ensure that the report is complete and correct. If any important information is missing or is unclear, queries will be raised. Investigators or other site personnel will inform PCG on any follow-up information on a previously reported SAE as soon as he or she becomes aware of it. Whenever an SAE is updated in Viedoc, a new e-mail alert will be sent.

The designated person at PCG will provide the medical monitor with an expectedness form for assessment of causality and expectedness. The medical monitor will provide his causality (unlikely, possibly or probably related to the blinded IMP) and expectedness (expected or unexpected) assessment. The reference documents for assessment of expectedness will be the IB for Immunose FLU, influenza antigen and saline, the SmPC for [REDACTED] and the prescribing information for [REDACTED].

Paper reporting

In case no internet access is available, the SAE should be reported using a paper copy of the SAE form, which will be available at the site. A scanned copy of the completed, signed and dated report should be faxed or e-mailed to:

PCG Clinical Services
Att. PCG SAE EUR003

[contact]

E-mail: [contact]

The site personnel should notify the medical monitor via phone or e-mail about the submission of the SAE report. As soon as there is internet access to Viedoc, the SAE should be reported electronically as well.

15.3.10 Reporting of suspected unexpected serious adverse events

The term SADR is used whenever either the Investigator or medical monitor deems the SAE as possibly or probably related to the IMP. Should an SADR be assessed as unexpected by the medical monitor, it is a SUSAR. Under such circumstances, an assigned, certified E2B reporter at PCG and the medical monitor will be unblinded. Based on treatment given, the medical monitor will reassess his causality treatment. In case the event is still regarded as a SUSAR, the E2B reporter at PCG will report the SUSAR to the CA, via the EudraVigilance database, and to the IEC in accordance with local regulations and PCGs SOPs within the following timelines:

- 7 calendar days if fatal or life-threatening (follow-up information within an additional 8 days)
- 15 calendar days if non-fatal and non-life-threatening (follow-up information as soon as possible)

The medical monitor is responsible for providing medical review to the SAE narrative in the Council for International organisations of medical sciences (CIOMS) form.

The Sponsor or designee also has the obligation to, once a year throughout the clinical study (or on request), submit a safety report to the CA and the IEC taking into account all new available safety information received during the reporting period.

The Sponsor is responsible for informing the Investigators concerned of relevant information about SUSARs that could adversely affect the safety of subjects.

